Official Title: A Novel Posttraumatic Stress Disorder Treatment for Veterans with Moral Injury

NCT Number: 03764033

Document Date: 10/23/2025

Study Protocol

Background: The prevalence of PTSD is estimated to be 12-15% in returning combat veterans, 1-3 and PTSD is now the most common mental health diagnosis among the youngest generation of veterans who use Veterans Health Administration care (55%), 4 Furthermore, veterans that have experienced trauma related to killing in war have high rates of suicide and more severe PTSD symptoms than those reporting other types of trauma(s). 5-7 As a result of killing in war, individuals may experience moral injury, which is defined as, "perpetrating, failing to prevent, bearing witness to, or learning about acts that transgress deeply held moral beliefs and expectations." A recent study found that PTSD and moral injury were distinct constructs with unique signs and symptoms, 7 and preliminary evidence indicates that the feelings of guilt and anger that characterize moral injury associated with killing may contribute to worsening symptoms over the course of existing treatments for PTSD. For these reasons, the development of targeted moral injury interventions is critical.

We have developed a treatment for moral injury called Impact of Killing (IOK), that is based on focus groups, quantitative studies, a moral injury framework, interviews with clinicians, and consultation with PTSD experts. ¹⁰ In our randomized, controlled pilot trial of IOK in veterans with PTSD, we found that compared to the wait-list control group, the IOK group experienced a significant improvement in PTSD symptoms, general psychiatric symptoms, and quality of life functional measures. ¹⁰

Objectives: The first aim of this project was to assess the efficacy of an individual treatment for PTSD stemming from moral injury called IOK. The primary outcome measure assessed self-reported psychosocial functioning (World Health Organization Quality of Life-BREF; WHOQOL-BREF). The secondary outcome measures examined clinician-assessed PTSD severity (Clinician Administered PTSD Scale for DSM-5; CAPS-5)¹² and self-report measures of PTSD (PTSD Checklist for DSM-5; PCL-5)¹³, guilt (Trauma-related Guilt Inventory; TRGI)¹⁴, and other mental health symptoms (Brief Symptom Inventory; BSI). Our second aim was to determine whether IOK gains made by veterans in treatment were durable, as measured by a six-month follow-up assessment of the self-report outcomes (i.e., WHOQOL-BREF, PCL-5, TRGI, and BSI).

Design: The study was a parallel design, randomized, controlled trial to test the efficacy of IOK, compared to a present-centered therapy (PCT) control condition. PCT has been used as a

comparison treatment in prior PTSD research trials. ¹⁶ To evaluate the durability of IOK gains, veterans also participated in a six-month follow-up visit to complete primary and secondary self-report outcome measures.

Methods: The study was managed by the principal investigator and research staff at the San Francisco VA Health Care System (SFVAHCS) and all recruitment, screening and data collection procedures were conducted by researchers at the James J. Peters VA Medical Center (JJPVAMC) in the Bronx, NY or the Durham VA Medical Center (DVAMC) in Durham, NC. Veterans between 18-82 years of age living in the continental U.S. were recruited through direct mailings, advertisements, and referrals from VA clinicians or other VA research studies. Interested veterans participated in an initial brief phone screen to ensure they met preliminary criteria. Those who passed the phone screen were invited to an in-person or video appointment to learn more about the study and complete consent procedures prior to additional screening. Participants completed demographic and medical history questionnaires, and a clinician-administered, mental health diagnostic interview (Structured Clinical Interview for DSM 5 [SCID-5]¹⁷ and CAPS-5). These diagnostic interviews were repeated at post-treatment. Veterans that passed the diagnostic interview were randomized to treatment. Study clinicians were clinical staff at one of the three study sites (SFVAMC, JJPVAMC, DVAMC).

A total of 100 veterans with moral injury were randomized 1:1 to either the IOK or PCT control arm within strata therapist treatment site (one of three locations) within randomly generated block sizes (4 and 6). IOK is a ten session individual psychotherapy, with 60- to 90-minute appointments conducted in-person or by video. PCT was matched for number and duration of treatment sessions. Primary and secondary self-report outcome measures were completed at baseline, mid-treatment, post-treatment and at six-month follow-up and the clinician diagnosed secondary outcome of PTSD severity (CAPS-5) was completed at baseline and post-treatment.

All participants randomized to treatment were included in the intent-to-treat analyses. Twelve of these individuals dropped out during treatment and 88 individuals completed study treatment. Of the treatment completers, one individual chose not to complete the self-report measures (i.e., WHOQOL-BREF, PCL-5, TRGI, and BSI) at the post-treatment time point and a different individual opted out of the post-treatment diagnostic interview (CAPS-5). As such, complete data for 87 responses through the post-treatment time point were included in the analyses.

Further, five of the 88 individuals that completed treatment were lost to follow-up and analyses of these data included complete data for 83 participants.

Statistical Analysis Plan: The primary and secondary outcome variables were analyzed with separate linear mixed models on the intent-to-treat sample, with participants as a random effect and fixed effects for treatment group (IOK, PCT), time point (baseline, mid-treatment, post-treatment, six-month follow-up), therapist treatment site (SFVAHCS, JJPVAMC, DVAMC), and the group-by-time interaction. Time point was treated as a categorical variable to avoid assumptions of linearity or any other functional form for outcome variables over time. Treatment effects were defined as the difference between treatment groups at the post-treatment time point, after adjusting for therapist site. IOK treatment durability was assessed using simple marginal contrasts comparing outcomes at the post-treatment to the follow-up time point.

Results: A total of 100 participants were randomized to study treatment and included in the intent-to-treat analysis (IOK=49; PCT=51). Participants ranged in age from 28 to 82 years (M=48.4 years); 98% were male (n=98) and 2% were female (n=2); 68% were Caucasian (n=68), 25% were Black/African American (n=25), 1% were Asian (n=1), 1% were American Indian or Alaska Native (n=1), 4% identified as multiracial or other (n=7), and 1% did not report their race (n=1). A total of 19% were Latino/Hispanic (n=19).

Participants randomized to IOK (n=49) reported statistically significant improvement on self-report measures of PTSD severity (p=.006) and guilt (p=.043) compared to veterans that were assigned to PCT (n=51). Furthermore, participants in the IOK arm continued to report greater improvement in self-reported PTSD (p=.008) and guilt (p=.028) at the six-month follow-up time point relative to the PCT arm. These results indicate that IOK treatment gains seen at post-treatment were maintained during the follow-up period. Further, veterans in the IOK group reported greater improvement in general mental health symptoms at six-month follow-up (p=.016) compared to the PCT group. There were no differences between groups on the primary (WHOQOL-BREF) or secondary (CAPS-5) outcomes, although both groups improved on these measures.

References:

- 2. Kang, H. K., Natelson, B. H., Mahan, C. M., Lee, K. Y., & Murphy, F. M. (2003). Post-traumatic stress disorder and chronic fatigue syndrome-like illness among Gulf War veterans: A population-based survey of 30,000 veterans. *American Journal of Epidemiology*, 157(2), 141-148.
- 3. Tanielian, T. L., Jaycox, L., & Rand Corporation. (2008). *Invisible wounds of war:*Psychological and cognitive injuries, their consequences, and services to assist recovery. Santa Monica, CA: RAND.
- Department of Veterans Affairs. (2015). Analysis of VA health care utilization among Operation Enduring Freedom (OEF), Operation Iraqi Freedom (OIF), and Operation New Dawn (OND) veterans. Retrieved from https://www.publichealth.va.gov/docs/epidemiology/healthcare-utilization-report-fy2015qtr1.pdf

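### Aim 2 is unanswered as planned: the SAP's post-treatment-to-six-month contrast is reported for none of the four outcomes, and the primary is the only one with no labelled six-month result

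*Combined protocol and SAP*

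**What the plan says.** Objectives. WHOQOL-BREF is the primary: "The primary outcome measure assessed self-reported psychosocial functioning (World Health Organization Quality of Life-BREF; WHOQOL-BREF"). The second aim concerns the durability of gains made under IOK, "as measured by a six-month follow-up assessment of the self-report outcomes (i.e., WHOQOL-BREF, PCL-5, TRGI, and BSI").

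Methods. All four measures were taken at the follow-up visit: "Primary and secondary self-report outcome measures were completed at baseline, mid-treatment, post-treatment and at six-month follow-up". The clinician-rated outcome was not: ("CAPS-5) was completed at baseline and post-treatment".

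Statistical Analysis Plan. Two different quantities are defined from the same mixed model. The treatment effect is between arms at one visit: "Treatment effects were defined as the difference between treatment groups at the post-treatment time point, after adjusting for therapist site". Durability is a comparison over time: "IOK treatment durability was assessed using simple marginal contrasts comparing outcomes at the post-treatment to the follow-up time point".

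Results. The six-month findings are IOK against PCT: p=.008 for PCL-5, p=.028 for TRGI and, for BSI, "Further, veterans in the IOK group reported greater improvement in general mental health symptoms at six-month follow-up (p=.016) compared to the PCT group". From the PCL-5 and TRGI comparisons the text concludes that the post-treatment gains held through follow-up. The primary appears once: "There were no differences between groups on the primary (WHOQOL-BREF) or secondary (CAPS-5) outcomes, although both groups improved on these measures".

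**The concern.** The follow-up result that is reported is not the one the plan defines for the follow-up question. The plan asks whether IOK participants kept what they had gained by the end of treatment. The Results instead say whether IOK participants were better off than PCT participants at six months. The claim that gains lasted is then drawn from the second quantity.

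The primary is in a weaker position still. It is first in the Aim 2 list and was collected at six months, yet no statement about it is tied to that visit.

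At stake is one of the trial's two stated aims. A reader would take durability as shown for PTSD symptoms and guilt when the planned evidence is not displayed. The same reader has nothing dated to six months on psychosocial functioning, the trial's primary outcome.

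**Working it through.** **Participant numbers.** Methods and Results: 49 + 51 = 100 randomized; 100 − 12 = 88 completed treatment; 88 − 5 = 83 with six-month data. The stated 83 reproduces, so follow-up data exist for the missing results.

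**Planned against reported.** Each Aim 2 outcome, matched to what the Results label by visit:

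| Outcome | Collected at six months | IOK vs PCT, post-treatment | IOK vs PCT, six months | IOK post-treatment to six months (planned for Aim 2) |
|---|---|---|---|---|
| WHOQOL-BREF (primary) | yes | undated null statement | none labelled | not reported |
| PCL-5 | yes | p=.006 | p=.008 | not reported |
| TRGI | yes | p=.043 | p=.028 | not reported |
| BSI | yes | none given | p=.016 | not reported |

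Planned durability contrast: 0 of 4. Labelled six-month between-arm result: 3 of 4, the exception being the primary.

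**Why one column cannot stand in for the other.** Write I1 and I2 for the IOK means at post-treatment and six months, and P1 and P2 for PCT. Then

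I2 − P2 = (I1 − P1) + (I2 − I1) − (P2 − P1).

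The reported six-month comparison is the left-hand side. The planned contrast is I2 − I1. A left-hand side that favours IOK is compatible with IOK participants losing ground after treatment, provided PCT participants lost ground too or the post-treatment gap was large enough to absorb the loss. Conversely, no difference between arms at six months is compatible with a fully kept gain in IOK. If the Results mean a difference in change from baseline, the same baseline difference is subtracted from both I2 − P2 and I1 − P1, and the argument is unchanged.

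**Dating the null sentence.** Three facts bear on it.
- It has no time point.
- It treats WHOQOL-BREF and CAPS-5 together, and CAPS-5 has no six-month measurement. The plan also defines treatment effects at post-treatment. Both point to post-treatment.
- It directly follows the six-month BSI sentence, so a reading that covers each visit at which each outcome was measured cannot be excluded.

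On either reading it compares arms, so it is not the planned contrast. The accompanying remark that both arms improved is also undated and does not isolate the period after treatment.

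**How much an undated null could say (illustration only).** Assume the 83 split 41/42, which the documents do not state, with no precision gained from repeated measures. The 95% CI half-width for a between-arm difference is 1.96 × √(1/41 + 1/42) = 0.43 SD. If the model recovered the precision of all 100, it would be 1.96 × √(1/49 + 1/51) = 0.39 SD. Without an estimate and interval, absence of a difference says little about the primary at six months.

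**The case against.** The strongest reply has four parts.

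First, the null sentence may be meant to cover six months, in which case the primary's follow-up result is disclosed. This stands in part: the time point is unstated, and post-treatment is only the more natural reading. It does not rescue Aim 2, because the sentence compares arms and gives no estimate, interval or p-value.

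Second, a lasting advantage over PCT is a reasonable thing to report, and arguably what clinicians want to know. That is true, and the fix keeps it. But it is not what the plan calls durability, and the plan puts the between-arm effect at post-treatment.

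Third, this is a reporting gap and not a design fault. The primary was named for follow-up, collected, and covered by a model with six months as a level of time. A short Results summary may be backed by fuller results elsewhere. This also stands as a description. The document nonetheless draws a durability conclusion, and what it shows does not support that conclusion.

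Fourth, a reader might infer that six-month results were chosen for display because they were significant. The documents do not support this. PCL-5, TRGI and BSI are all of the secondary outcomes collected at that visit, so none was left out. The pattern rests on a single outcome, whose null is disclosed in the same section at an unstated time. The documents also state no significance level.

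**Conclusion.** The point holds as a mismatch between the planned and the reported follow-up analysis. The contrast that the plan assigns to Aim 2 is shown for none of four outcomes, and the statement that gains lasted is drawn from comparisons of a different kind. WHOQOL-BREF is the only one of the four without a labelled six-month result.

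Three stronger readings are tempting and should be avoided. It is not shown that the primary went unanalysed at six months, or that IOK gains on it faded; the documents are silent on both. Nor is the gap confined to the primary: saying so would imply that Aim 2 is answered for PCL-5, TRGI and BSI, and it is not.

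The size is best given as the counts above. Effect sizes back-calculated from the three six-month p-values would describe the secondaries and not the missing contrasts. The conclusion rests on reading the plan's durability contrast as within IOK, as its wording and Aim 2 both indicate. It does not depend on how the null sentence is dated.

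**What to change.** From the models already fitted:

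1. Report the IOK contrast of six months against post-treatment, with a 95% CI, for WHOQOL-BREF first and then PCL-5, TRGI and BSI. Base the durability conclusion on these. Where the contrast does not support it, limit the statement to the between-arm finding at six months.
2. Report the six-month IOK-minus-PCT difference with a 95% CI for all four outcomes, labelled as additional to the treatment effect that the plan defines.
3. State the time point of the sentence reporting no differences on WHOQOL-BREF and CAPS-5. If it covers six months for WHOQOL-BREF, say so separately from CAPS-5.

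No new data and no new model are needed. The cost is a few more lines of results and the possibility that the follow-up summary becomes less favourable to IOK.

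### Participant is the only random term stated, which ordinarily assumes equal variance and equal correlation across visits; an unstructured covariance would remove that unchecked assumption cheaply

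*Combined protocol and SAP*

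**What the plan says.** The Statistical Analysis Plan paragraph fits a separate linear mixed model to each outcome, "with participants as a random effect and fixed effects for treatment group (IOK, PCT), time point (baseline, mid-treatment, post-treatment, six-month follow-up", together with therapist site and the group-by-time interaction. Participant is the only random term. No residual covariance structure, random slope, robust SE or degrees-of-freedom method is named.

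On time, the same paragraph says: "Time point was treated as a categorical variable to avoid assumptions of linearity or any other functional form for outcome variables over time". It then fixes the two contrasts of interest. The treatment effect: "Treatment effects were defined as the difference between treatment groups at the post-treatment time point, after adjusting for therapist site". Durability: "IOK treatment durability was assessed using simple marginal contrasts comparing outcomes at the post-treatment to the follow-up time point".

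Self-report outcomes have four visits. CAPS-5 has two: "the clinician diagnosed secondary outcome of PTSD severity (CAPS-5) was completed at baseline and post-treatment".

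Results gives p-values without estimates, SEs or SDs. IOK participants "reported statistically significant improvement on self-report measures of PTSD severity (p=.006) and guilt (p=.043" relative to PCT, and there was "greater improvement in self-reported PTSD (p=.008) and guilt (p=.028) at the six-month follow-up time point". General mental health symptoms at six months have p=.016. For the rest: "There were no differences between groups on the primary (WHOQOL-BREF) or secondary (CAPS-5) outcomes". No significance level or sidedness is stated.

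**The concern.** A participant random effect with nothing else specified is ordinarily a random intercept with independent, constant-variance residuals. That forces one variance at all visits and one correlation between all pairs of visits, across a span running from before a ten-session therapy to six months after it. The plan takes care to make no assumption about the shape of the means, but it gives the covariance no such protection and reports no check of it.

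The two contrasts are exposed differently. The SE of the post-treatment group difference depends mainly on whether the post-treatment variance equals the average over visits. The SE of the post-to-follow-up contrast also depends on whether the correlation between those two visits equals the average over all pairs. An SE that is too large there would make a loss of gains harder to detect, and durability is the trial's second aim. Every between-arm p-value in Results rests on SEs of this kind.

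**Working it through.** **Inputs from the document.** Four visits for self-report outcomes; 49 and 51 randomized; 12 dropouts, 87 responses through post-treatment, 83 at follow-up; the five p-values in Results. **Assumed:** a two-sided .05 level; .043 is the post-treatment group difference; all SDs and correlations below, with the same covariance in both arms. The p-values cannot be reproduced because no estimate or SE is reported.

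**1. SE margin of each reported result.** With the estimate held fixed, the factor by which the SE must grow to reach p=.05 is z(p)/1.960.

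| Result | p | z | factor |
|---|---|---|---|
| Guilt, post-treatment | .043 | 2.024 | 1.033 |
| Guilt, six months | .028 | 2.197 | 1.121 |
| General symptoms, six months | .016 | 2.409 | 1.229 |
| Self-reported PTSD, six months | .008 | 2.652 | 1.353 |
| Self-reported PTSD, post-treatment | .006 | 2.748 | 1.402 |

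With t on 85 df the guilt post-treatment factor is still 1.033. Over the rounding range .0425 to .0435 it is 1.035 to 1.030.

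**2. Post-treatment difference.** With complete data a random-intercept model pools variance over visits, so true SE / model SE = sqrt(post-treatment variance / mean visit variance). Correlation does not enter.

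- SDs 1, 1.1, 1.2, 1.2: sqrt(1.44 / [(1 + 1.21 + 1.44 + 1.44)/4]) = sqrt(1.44/1.2725) = 1.064, so the model SE is too small.
- SDs 1, 1.2, 1.2, 1.2: sqrt(1.44/1.33) = 1.041, too small.
- SDs 1, 0.9, 0.9, 0.9: sqrt(0.81/0.8575) = 0.972, so the model SE is too large.

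Setting the ratio to 1.033 gives the SD growth from baseline to post-treatment that would bring guilt to .05. It is 7% if post-treatment and follow-up both rise, 9% if mid-treatment is halfway and later visits are flat, 15% if all later visits rise equally, and 16% if growth is linear. Weighting visits by counts 100/94/87/83 (94 is assumed) gives 6-14%.

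**3. Durability contrast.** With equal SDs and complete data, model SE / true SE = sqrt[(1 - mean correlation)/(1 - post/follow-up correlation)]. Assumed correlations: baseline-mid .6, baseline-post .45, baseline-follow-up .4, mid-post .7, mid-follow-up .6 (sum 2.75).

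- Post/follow-up .55: mean 3.30/6 = .550; sqrt(.450/.450) = 1.00.
- .65: mean 3.40/6 = .567; sqrt(.433/.350) = 1.11.
- .75: mean 3.50/6 = .583; sqrt(.417/.250) = 1.29.

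**4. Simulation with missing data.** 4,000 null trials per scenario, 49/51, three sites, REML for both models. Data were missing completely at random at the trial's counts, with half the dropouts assumed also to miss mid-treatment. The correlations are those in step 3, with post/follow-up .65 unless shown; the first row sets all of them to .55. Degrees of freedom were approximate (250 for the stated model, 85-90 for unstructured), not Kenward-Roger. Monte Carlo error is about 0.35 points.

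| Scenario (type I error) | Stated model | Unstructured |
|---|---|---|
| Post-treatment; stated model true | 5.1% | 4.9% |
| Post-treatment; SD ratio 1.2, mid halfway | 6.7% | 4.9% |
| Post-treatment; SD ratio 1.2, all later visits | 6.4% | 5.2% |
| Post-treatment; SD ratio 0.9, all later visits | 4.4% | 5.1% |
| Post-treatment; equal SDs, post/follow-up .55 or .75 | 5.2% | 5.3% |
| Durability; equal SDs, post/follow-up .55 | 5.7% | 5.4% |
| Durability; equal SDs, post/follow-up .75 | 1.8% | 5.5% |

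For durability, model SE over empirical SE was 0.99 at .55 and 1.25 at .75.

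**5. A refit also moves the estimate.** The mean absolute shift in the post-treatment estimate was 0.032 SE when the stated model was true and 0.068-0.078 SE otherwise. The guilt margin is 2.024 - 1.960 = 0.064 SE.

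**The case against.** The strongest reply is that no error is shown. The document gives no SD, correlation, estimate or SE, so every magnitude beyond the p-to-z conversion rests on assumed inputs. That stands, and it is why this is a cheap improvement and not a demonstrated mistake. The document does suggest one reason for spread to grow, entry on the diagnostic interview, but that bears on CAPS-5, where no group difference was reported, and not on guilt.

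A reader might infer that the guilt result at post-treatment is an artefact of an understated SE. The document does not support this: the direction is unknown, and .043 is borderline under almost any change of model. Even when the stated model is exactly right, the refit shifts the estimate by about half the guilt margin on average, so crossing .05 would not by itself show misspecification. A post-only rise in spread would give more striking figures (4% SD growth to reach .05; 9.2% type I error at ratio 1.2). Nothing in the document suggests spread that rises at one visit and then returns, so those figures carry no weight here.

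It is also not certain which contrast .043 tests. The plan defines a difference at post-treatment, whereas Results speaks of improvement. If change from baseline was tested, correlation matters too. With equal SDs and correlation .75 per visit step, the SE factor is sqrt[(1 - .5625)/(1 - .6328)] = 1.09, giving p=.064. That is a further reason to state the model and contrast.

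Finally, a richer structure may have been fitted and not described. In that case the defect is one of reporting, because the SEs cannot be reproduced from the plan.

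**Conclusion.** The point holds as a cheap improvement. The stated model ordinarily imposes equal variance and equal correlation across visits, and the plan neither justifies nor checks this. The durability contrast is the more exposed of the two: on the assumed correlations its SE ranges from about right to 25-29% too large. For the post-treatment difference, a sustained SD ratio of 1.2 gives about 6.4-6.7% type I error against about 5% with an unstructured covariance. A ratio of 0.9 makes the stated test conservative, and unequal correlation alone has almost no effect.

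Among reported results, only guilt at post-treatment lies within a 3% change in SE, assuming a two-sided .05 level and that .043 is the post-treatment difference. The others have margins of about 12-40%.

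Two stronger conclusions do not follow. The null WHOQOL-BREF and CAPS-5 results are not products of a too-liberal test. And no reported durability figure is challenged, because Results gives between-arm p-values at six months and no post-to-follow-up contrast; what is affected is the plan's stated durability test.

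**What to change.** Fit an unstructured within-participant covariance over the visits (four for self-report outcomes, two for CAPS-5) by REML with Kenward-Roger degrees of freedom. Report the SD at each visit and the between-visit correlations. Give the post-treatment and post-to-follow-up contrasts with 95% confidence intervals. Because the results are already known, present this beside the original model as a sensitivity analysis, whichever way it falls, and say whether guilt at post-treatment stays below .05. If a richer structure was already fitted, state it in the Statistical Analysis Plan paragraph.

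The cost is a few lines of code and text, with no new data. The covariance parameters rise from 2 to 10 for four-visit outcomes (8 more) and from 2 to 3 for CAPS-5 (1 more). If the stated model is right, intervals are about 1% wider (0.4-1.1% across simulations).

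### The outcome models adjust for therapist site but have no term for the treating therapist, so the standard errors behind the positive secondary results may be understated, depending on how therapists were allocated to arms.

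*Combined protocol and SAP*

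**What the plan says.** The Statistical Analysis Plan paragraph gives the whole model: "with participants as a random effect and fixed effects for treatment group (IOK, PCT"), then time point, "therapist treatment site (SFVAHCS, JJPVAMC, DVAMC), and the group-by-time interaction". The effect is specified as follows: "Treatment effects were defined as the difference between treatment groups at the post-treatment time point, after adjusting for therapist site". Site is therefore the only provider-related term, and participant is the only random effect.

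On delivery, Methods says "Study clinicians were clinical staff at one of the three study sites (SFVAMC, JJPVAMC, DVAMC"). It describes the two treatments thus: "IOK is a ten session individual psychotherapy, with 60- to 90-minute appointments conducted in-person or by video", and "PCT was matched for number and duration of treatment sessions". Participants were "randomized 1:1 to either the IOK or PCT control arm within strata therapist treatment site (one of three locations"), so site was a stratum and therapist was not.

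The documents do not give the number of therapists, their caseloads, whether a therapist delivered one treatment or both, or how participants were assigned to therapists. They describe no therapist-level sensitivity analysis.

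**The concern.** In a psychotherapy trial the therapist is part of what is delivered, and participants treated by the same therapist may have correlated outcomes. The participant random effect handles repeated visits by one person. The site effect removes average differences between three locations. Neither covers dependence between participants who share a therapist within a site.

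Two things could follow for the IOK-PCT contrast. Its standard error could be too small, and an unusually effective therapist in one arm could look like an effect of IOK content. The second matters because the stated matching of PCT covers session number and length only.

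The Results section reports no group difference on the primary outcome or CAPS-5, so the positive claims rest on five secondary self-report p-values. Several of these are not far below .05.

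**Working it through.** The documents give no therapist ICC, caseload, alpha or design calculation, so there is no planned figure to reproduce. What follows is a sensitivity range on assumed values, at an assumed two-sided level of .05.

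**Inputs from the documents.** The analysis was "included in the intent-to-treat analysis (IOK=49; PCT=51"). Complete data were available for 87 participants through post-treatment and 83 at six months. Reported p-values are: post-treatment PCL-5 .006 and guilt (TRGI) .043; six-month PCL-5 .008, guilt .028 and BSI .016.

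**Assumed inputs.** Within-site therapist ICC is 0.01 to 0.05, since site is already adjusted for. Each therapist has m = 5 to 12 observed participants, all in one arm.

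**Step 1: back to t.** With df = 87 - 2 = 85 and 83 - 2 = 81, the two-sided p-values give t = 2.819 (PCL-5 post), 2.054 (guilt post), 2.719 (PCL-5 six-month), 2.238 (guilt six-month) and 2.461 (BSI six-month).

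**Step 2: inflate.** Design effect DE = 1 + (m - 1) x ICC; adjusted t = t / sqrt(DE). For ICC 0.05 and m = 8, DE = 1 + 7 x 0.05 = 1.35 and sqrt(DE) = 1.162. Post-treatment guilt becomes 2.054 / 1.162 = 1.768, p = .081.

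| ICC, m | DE | PCL-5 post | Guilt post | PCL-5 6 mo | Guilt 6 mo | BSI 6 mo |
|---|---|---|---|---|---|---|
| reported | 1.00 | .006 | .043 | .008 | .028 | .016 |
| 0.01, 5 | 1.04 | .007 | .047 | .009 | .031 | .018 |
| 0.02, 8 | 1.14 | .010 | .058 | .013 | .039 | .024 |
| 0.05, 8 | 1.35 | .017 | .081 | .022 | .058 | .037 |
| 0.05, 12 | 1.55 | .026 | .103 | .032 | .076 | .052 |

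**Step 3: break-even.** The DE at which a result reaches .05 is (t / critical t) squared. For post-treatment guilt it is (2.054 / 1.988)^2 = 1.07, which is the DE at ICC 0.01 and m = 8. With critical t = 1.990 at six months, guilt breaks even at about 1.26 and BSI at about 1.53.

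**Step 4: degrees of freedom.** The table keeps 85 and 81 df. With therapists nested in arm, df depend on the number of therapists. At m = 8 there would be about 87 / 8 = 11 therapists. Removing the intercept, arm and two site terms leaves roughly 11 - 4 = 7 df. At ICC 0.05, post-treatment PCL-5 is then about .046 instead of .017, and guilt about .12 instead of .081. The table is therefore a lower bound for the nested case.

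**Step 5: does allocation matter?** A null simulation used 96 participants, three sites, a site-adjusted linear model on one post-treatment score, therapist ignored, and total therapist variance share 0.02 to 0.10. Type I error at nominal .05 was:
- nested in arm: 0.092-0.236 with one therapist per site per arm, 0.066-0.142 with two, and 0.055-0.088 with four;
- crossed with arm, balanced, no therapist-by-arm variation: 0.041-0.053;
- crossed, with half of the therapist variance varying by arm: 0.051-0.156.

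**The case against.** The strongest reply is that the consequence depends on facts the documents do not give. A reader might infer that the reported p-values are too small, or that the guilt and PTSD differences are really therapist effects. The documents support neither. If each therapist carried a balanced caseload in both arms, therapist main effects cancel from the contrast, and the simulation shows no inflation. Only therapist-by-arm variation or imbalance would remain. This objection stands, and the point is conditional because of it.

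A reader might also take it as stated that PCT was delivered individually. Only IOK is described that way. For PCT it is a reasonable inference from the session matching and the shared therapist-site factor.

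Third, the ICC and caseloads are assumed. At ICC 0.01 and m = 5 no claim changes. At ICC 0.05 and m = 8, with df unchanged, only the two guilt results cross .05. This also stands, although therapist-based df would push p-values up further.

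Finally, larger standard errors cannot overturn null results, so the primary conclusion is unaffected.

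None of this removes the omission. The model as written treats participants who share a therapist as independent, and the documents do not let a reader tell whether that is harmless.

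**Conclusion.** The concern holds in conditional form. The missing therapist term is certain, but whether it matters depends on allocation. Understated standard errors, and therapist differences read as treatment effects, are possible if therapists were nested in arm, if their effects differ by arm, or if caseloads were unbalanced. With balanced, crossed therapists and no therapist-by-arm variation, there is little or no inflation.

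The exposed claims are the secondary self-report ones. Over the assumed range (ICC 0.01-0.05, m = 5-12, nested, df 85 or 81), post-treatment guilt runs from .047 to .103, six-month guilt from .031 to .076, six-month BSI from .018 to .052, post-treatment PCL-5 from .007 to .026 and six-month PCL-5 from .009 to .032. The guilt finding at post-treatment is fragile. The PCL-5 findings are sturdier but not immune once df reflect a small number of therapists.

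**What to change.** As a sensitivity analysis reported beside the current results, refit each outcome model with a random effect for treating therapist.

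- **Timing.** Let the effect act on post-baseline visits only, or as therapist-by-time. Baseline precedes therapy, so an intercept held constant over all visits would force a therapist effect where none can exist. It would also cancel from any change-from-baseline contrast.
- **Structure.** Nest therapist in arm if therapists delivered one treatment. Use therapist plus therapist-by-arm if they delivered both.
- **Inference.** Use Kenward-Roger or Satterthwaite degrees of freedom.
- **Reporting.** State the number of therapists, caseloads by arm, nested or crossed delivery, the therapist ICC, and the refitted estimates and confidence intervals. Qualify any secondary claim that does not hold up.

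The cost is modest: therapist assignment should already be in the treatment records, so no new participant data are needed. The downside is wider intervals, possibly far fewer degrees of freedom, and a therapist variance that is unstable or estimated at zero if therapists were few. That is why this should be a sensitivity analysis and not a replacement for the main one.
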